5.3.4 Lirilumab Discontinuation Criteria

Treatment should be permanently discontinued for the following:

- Any Grade 2 drug-related uveitis or eye pain or blurred vision that does not respond to topical therapy and does not improve to Grade 1 severity within the re-treatment period OR lasting > 7 days with systemic treatment
- Any Grade 3 non-skin, drug-related adverse event lasting > 7 days, with the following exceptions for drug-related laboratory abnormalities, uveitis,

pneumonitis, bronchospasm, diarrhea, colitis, neurologic adverse event, hypersensitivity reactions, and infusion reactions:

- Grade 3 drug-related uveitis, pneumonitis, bronchospasm, diarrhea, colitis, neurologic adverse event, hypersensitivity reaction, or infusion reaction of any duration requires discontinuation
- Grade 3 drug-related laboratory abnormalities do not require treatment discontinuation except those noted below:
- Any drug-related liver function test (LFT) abnormality that meets the following criteria require discontinuation: AST or ALT > 8 x ULN
- Any Grade 4 drug-related adverse event or laboratory abnormality, except for the following events which do not require discontinuation:
 - Isolated Grade 4 amylase or lipase abnormalities that are not associated with symptoms or clinical manifestations of pancreatitis and decrease to < Grade 4 within 1 week of onset.
 - Isolated Grade 4 electrolyte imbalances/abnormalities that are not associated with clinical sequelae and are corrected with supplementation/appropriate management within 72 hours of their onset
- Any dosing interruption lasting > 8 weeks with the following exceptions:
 - Dosing interruptions to allow for prolonged steroid tapers to manage drug-related adverse events are allowed. Prior to re-initiating treatment in a subject with a dosing interruption lasting > 8 weeks the Investigator must be consulted. Tumor/Leukemia assessments should continue as per protocol even if dosing is interrupted.
 - Dosing interruptions > 8 weeks that occur for non-drug-related reasons may be allowed if approved by the Investigator. Prior to re-initiating treatment in a subject with a dosing interruption lasting > 8 weeks the Investigator must be consulted. Tumor/Leukemia assessments should continue as per protocol even if dosing is interrupted.

5.3.5 Detailed management algorithms for immune-oncology drug-related adverse events (including gastrointestinal, renal, pulmonary, hepatic, endocrine, skin and neurological) are provided in Appendix G. These general guidelines constitute guidance to the Investigator and may be supplemented by discussions with the Medical Monitor representing the Sponsor in specific cases.

5.3.6 Intra-patient dose re-escalation of 5-azacytidine for patients who have had dose-reductions due to hematological or non-hematological toxicity:

Once the MTD has been established in the lead-in, the lirilumab dose will not be reduced or escalated during the phase II. Intra-patient dose re-escalation of 5-azacytidine (in accordance with the dosing schema in table 1) will be permitted provided:

- Patient has completed ≥ 1 cycle at their current dose level
- Patient has not experienced any grade 3 or higher non-hematologic drug-related toxicity, and
- Patient has not experienced drug-related hematologic DLT, and
- At least 6 patients have been treated at the next higher dose level and followed for at least 28 days without experiencing DLT.
- The dose may be escalated by one dose level per cycle (per table 1) provided such dose level does not exceed the established MTD or dose level 0, whichever is lower. Dose level 0 is the maximum dose allowed on this study. No dose escalation beyond dose level 0 will be permitted.

5.3.7 Modifications of dose schedules other than the above will be allowed within the following guidelines:

5.3.7.1 Further dose reductions can be made to keep clinically significant toxicities grade ≤ 2 .

5.3.7.2 Dose adjustments by more than 1 dose level at a time (e.g., from 5-azacytidine 75 mg/m² to 25 mg/m²) can be considered when judged in the best interest of the patient (e.g. severe myelosuppression) when toxicity has resolved. The reason for this reduction will be discussed with the PI or Co-PI and documented in the medical record.

5.3.7.3 A patient who has had a dose reduction because of any of the reasons mentioned above may have their dose escalated provided the patient has remained free of toxicity requiring dose adjustments as defined above for at least 1 month. Escalation will be made by 1 dose-level increment only, and not more frequent than every month.

5.3.7.4 Treatment interruptions and dose modifications other than the ones mentioned above for either study drug related toxicity and/or events that are unrelated to study drug, for example but not limited to hospitalization for reasons unrelated to study drug can be considered after discussion with the PI, and proper documentation of the rationale. Dose adjustment/delay of only one of the agents is permissible if the toxicity is most likely judged to be related to one of the agents by the investigator (e.g., in patients with autoimmune thyroiditis or autoimmune hepatitis this would be likely secondary to lirilumab and 5-azacytidine dose could be escalated, in patients with cytopenia's this would be likely secondary to 5-azacytidine and lirilumab dose could be escalated).

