5.3.2 Lirilumab and 5-azacytidine dose adjustments for non-hematologic drug-related AEs

Investigators should, whenever possible, determine which medication is causing the toxicity and interrupt or dose reduce 5-azacytidine and/or interrupt lirilumab, as applicable. No dose reductions (only interruptions) are permitted for lirilumab. Dose reductions of azacytidine will be as per Table 1. Thus, if dose level 0 is established as the MTD, one and two dose level reductions of azacytidine will be azacytidine 50 mg/m² x 7 days and azacytidine 25 mg/m² x 7 days, respectively. If the MTD is below dose level 0 further dose reduction levels of 5-azacytidine will be defined before moving to the phase II portion of the study.

Table 2 Dose adjustments for non-hematologic drug-related adverse events, clinically significant in the opinion of the investigator

Grade	Occurrence	Dose modification
1 or 2	Any time	No dose reduction.
3 or 4 (Persistent grade 2: Consider similar dose adjustments if persistent and not responding to optimal management in the opinion of PI and treating physician)	1st and 2nd time	Hold lirilumab and 5-azacytidine. Resume lirilumab and 5-azacytidine at prior dose if recovery to ≤ Grade 1 occurs within 14 days. If toxicity persists for 15-28 days, hold therapy and resume at ONE dose level below current dose for 5-azacytidine and prior dose of lirilumab ONLY after recovery to ≤ Grade 2. Dose re-escalation to prior dose of 5-azacytidine is permitted in accordance with the dose-escalation guidelines in section 5.3.6.
	3 rd and 4th time	Hold lirilumab and 5-azacytidine. Follow until toxicity ≤ Grade 2. Resume lirilumab at prior dose and 5-azacytidine at ONE dose level below current dose. Dose re-escalation of 5-azacytidine to prior dose is permitted in accordance with the dose-escalation guidelines in section 5.3.6.
	5th time	Hold lirilumab and 5-azacytidine. Follow until toxicity ≤ Grade 2. Resume lirilumab at prior dose and 5-azacytidine at TWO dose levels below current dose. Dose re-escalation of 5-azacytidine by ONE dose level every 4 weeks is permitted in accordance with the dose-escalation guidelines in section 5.3.6.

5.3.3 Lirilumab dose delay/interruption for immune-oncology drug-related AEs, clinically significant in the opinion of the investigator

Lirilumab administration should be delayed for the following drug-related AEs, clinically significant in the opinion of the investigator:

- Any Grade ≥2 non -skin AE, except that

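### Table 2 resumes lirilumab at the prior dose after some events for which Section 5.3.4 requires permanent discontinuation, and the visible text does not say which rule governs

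*Combined protocol and SAP*

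**What the plan says.** **Section 5.3.2 and Table 2.** The table applies to non-hematologic drug-related events that the investigator judges clinically significant. For Grade 3 or 4 events it holds both drugs and then gives four resume instructions:

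- 1st or 2nd time, quick recovery: "Resume lirilumab and 5-azacytidine at prior dose if recovery to ≤ Grade 1 occurs within 14 days".
- 1st or 2nd time, toxicity lasting 15 to 28 days: 5-azacytidine one level down, and "prior dose of lirilumab ONLY after recovery to ≤ Grade 2".
- 3rd or 4th time, once at Grade 2 or lower: "Resume lirilumab at prior dose and 5-azacytidine at ONE dose level below current dose".
- 5th time, once at Grade 2 or lower: "Resume lirilumab at prior dose and 5-azacytidine at TWO dose levels below current dose".

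**Section 5.3.4.** The lead-in reads "Treatment should be permanently discontinued for the following". The criteria that matter here are:

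- "Grade 3 drug-related uveitis, pneumonitis, bronchospasm, diarrhea, colitis, neurologic adverse event, hypersensitivity reaction, or infusion reaction of any duration requires discontinuation".
- "Any Grade 3 non-skin, drug-related adverse event lasting > 7 days". Laboratory abnormalities are handled separately: at Grade 3 they do not require stopping unless AST or ALT exceeds 8 x ULN.
- "Any Grade 4 drug-related adverse event or laboratory abnormality, except for the following events which do not require discontinuation". The exceptions are isolated amylase or lipase abnormalities and isolated electrolyte abnormalities, each under stated conditions.

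Table 2 refers three times to Section 5.3.6, for 5-azacytidine re-escalation. It does not refer to 5.3.3 or 5.3.4.

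**The concern.** The two rules overlap, and in the overlap they give opposite instructions about the same drug. A clinician who follows Table 2 as written re-exposes a patient to an investigational antibody after an event for which another section of the same protocol requires a permanent stop. The permissive rule sits in the table that staff are likely to consult when an event occurs.

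There is also a compliance problem. Section 9.3 lists noncompliance with discontinuation criteria as a class of violation or deviation. A physician could do exactly what Table 2 says and still be in breach of 5.3.4.

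The worked event is plausible. Section 2.4 reports one related Grade 3 bronchospasm in the blinded lirilumab-or-placebo maintenance trial. The arm is not stated, so this shows that the event can arise and says nothing about how often.

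**Working it through.** No figure in the plan is at issue, so the check sets the two rules side by side. All events below are drug-related, non-hematologic and clinically significant. The first five rows assume a 1st or 2nd occurrence.

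| Event | Table 2 | Section 5.3.4 | Conflict? |
|---|---|---|---|
| Grade 3 bronchospasm, Grade 1 within 14 days | Resume lirilumab, prior dose | Stop (named type, any duration) | Yes |
| Grade 3 colitis, Grade 1 by day 5 | Resume, prior dose | Stop (named type, any duration) | Yes |
| Other Grade 3 non-skin, non-laboratory event, at Grade 3 for 10 days, Grade 1 by day 14 | Resume, prior dose | Stop (10 > 7 days) | Yes |
| Grade 4 event outside the exceptions, Grade 1 within 14 days | Resume, prior dose | Stop | Yes |
| Any of these types persisting beyond 28 days | No resume instruction | Stop | No |
| Grade 3 skin event | Resume | No Grade 3 stopping criterion | No |
| Other Grade 3 non-skin event, 7 days or less, not a named type | Resume | Not a stopping event | No |
| Grade 3 laboratory abnormality with AST and ALT not above 8 x ULN | Resume | Not a stopping event | No |

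**Extent of the overlap.** A conflict needs both a 5.3.4 criterion and a Table 2 resume instruction. For a 1st or 2nd occurrence, the instruction exists for recovery within 14 days or persistence of 15 to 28 days. For the 3rd to 5th occurrences, it exists once the event is at Grade 2 or lower. For Grade 3 non-skin, non-laboratory events off the named list, the conflict starts when the Grade 3 phase passes 7 days. That can happen in the 14-day branch (days 8 to 14) and in the 15-to-28-day branch.

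**Does attribution remove it?** Suppose drug-related in 5.3.4 means lirilumab-related only. Table 2 does not exclude lirilumab-related events, so the bronchospasm case still falls under both rules. The instruction in 5.3.2 to identify the responsible drug does not help: lirilumab would be interrupted, and Table 2 would then resume it.

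**Does any visible text rank the rules?**

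- Section 5.2.1 points to 5.3 as a whole.
- Section 5.3.3 refers twice to the discontinuation section, for combined liver values and for delays over 8 weeks. Neither reference mentions Table 2.
- Section 5.3.5 describes the Appendix G algorithms as guidance.
- Section 5.3.7.4 covers modifications beyond those already listed.
- Sections 9.1.2 and 9.1.3 allow stopping on the investigator's judgment.

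None of these gives either rule precedence.

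**Does it reach the statistical design?** The DLT window is the first 28 days. In the lead-in, cycle 2 may not start before then, and lirilumab is given once per cycle. Resumption therefore falls outside the DLT window. For the toxicity boundary in Table 4, a patient with a drug-related Grade 3/4 event is already counted, and the count is of patients.

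**The case against.** The strongest reply is that the specific rule overrides the general one. Table 2 is a dose-adjustment table for both drugs, while 5.3.4 is headed as the lirilumab discontinuation criteria and uses mandatory language. Stopping is always permitted under 9.1.2 and 9.1.3, and 5.3.3 already treats 5.3.4 as the place where permanent stopping is decided. Table 2 also keeps a proper role for 5-azacytidine-attributed events, Grade 3 skin events, short Grade 3 events off the named list and most Grade 3 laboratory abnormalities.

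Much of this stands. It is the likeliest account of intent, and it shows that a cautious investigator has cover to stop. But it is an inference. Table 2 is itself a lirilumab rule, since its section heading names the drug and every resume instruction covers its dose. The immune-oncology qualifier that might separate the scopes is in the 5.3.3 heading and is absent from 5.3.4.

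Two further objections succeed and limit the point. First, a reader might infer that the named Grade 3 types conflict with Table 2 whatever their duration. They do not: for a 1st or 2nd event persisting past 28 days Table 2 gives no resume instruction. Second, a reader might count the lower recovery thresholds in Table 2 (Grade 2 or lower in three of four instructions, against generally Grade 1 or baseline in 5.3.3) as a second contradiction. That difference may partly reflect the immune-oncology scope of 5.3.3, so it is not pressed here.

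**Conclusion.** The inconsistency is real and should be fixed. Every resume instruction in Table 2 restarts lirilumab at the prior dose, and none excludes events that meet a 5.3.4 stopping criterion.

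Its size can be stated only as the set of events affected. The documents give no basis for a frequency. A reader might take maximum enrolment as the number affected: 24 lead-in patients plus 40 - 6 = 34 more gives 58, before replacements. That is a ceiling on who could be treated under both rules, assuming 5.3 applies to both parts. A lead-in that ends after two cohorts of 6 would give 12 + 34 = 46. Neither figure counts patients with a conflicting event.

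A reader might also infer that dose finding or toxicity monitoring is compromised. The documents do not support that: DLT counts, the MTD, the boundaries and the sample size are unchanged.

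The conclusion rests on the visible text. Appendices E (Investigator Brochure), G (management algorithms) and I (dosing manual) were not available. Section 6.1 sends treatment of infusion reactions to Appendix I, so that document may bear on infusion reactions, and possibly on hypersensitivity and bronchospasm.

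**What to change.** Add one sentence to Table 2: *Resumption of lirilumab is subject to 5.3.4 (and to 5.3.3 for immune-oncology drug-related events); if a 5.3.4 criterion is met, lirilumab is permanently discontinued and not resumed.*

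Optionally, replace the word Treatment with Lirilumab in the 5.3.4 lead-in, in line with its heading, if that is what the sponsor intends. This needs a sponsor decision on whether 5-azacytidine may continue. No new attribution rule is needed.

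The cost is a short amendment, with no change to endpoints, sample size or boundaries. The downside is that a few patients who might have been re-treated under Table 2 will stop lirilumab, which 5.3.4 already requires.

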5.2 Schedule

The Investigator is responsible for completing the cohort summary template and submitting to the IND office Medical Monitor for review and approval prior to advancing subjects to the next protocol specified cohort/dose level. A copy of the cohort summary should be placed in the Investigator's Regulatory Binder under "sponsor correspondence". This should be submitted after the first six patients.

5.2.1 Patients will be treated according to the following schedule:

- 5-azacytidine will be administered subcutaneously (SQ) or intravenously (IV) for 7 days of every cycle (Days 1-7) as determined by treating physician. Both SQ and IV forms of administration are FDA approved and considered interchangeable. Patients may start receiving 5-azacytidine by one route and changed to the other at any time as needed based on patient and/or physician preference.
- Lirilumab will be administered as an approximately 60 minute IV infusion on Day 8 (+/-2 days) of each 5-azacytidine cycle. Lirilumab will be administered every cycle with no interruptions unless there are adverse events as described in Section 5.3. The dosing calculations should be based on the body weight. All doses should be rounded to the nearest milligram. There will be no dose reductions (only interruptions when indicated) allowed for lirilumab on this trial.

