5.2.1.1 The starting dose will be dose level -1.

Table 1. Dose levels of 5-azacytidine and lirilumab during the lead-in phase (part a)

Dose level	5-azacytidine (mg/m ² /d, Days 1-7)	Lirilumab (mg/kg, day 8)
-4	25	0.3
-3	50	0.3
-2	75	0.3
-1	75	1.0 (Starting dose)
0	75	3.0

5.2.1.2 The goal of the lead-in phase is to identify the dose at which <2/6 patients experience DLT. During the lead-in phase the dose’s of 5-azacytidine and lirilumab may be reduced if 2 or more patients experience DLT at any given dose. After the lead in phase the dose of lirilumab may not be reduced in the phase II portion of the study. For potential lirilumab related AEs in the phase II portion of the study only dose interruptions of lirilumab will be permitted. Dose reductions or escalations of 5-azacytidine will continue to be permitted in the phase II portion of the study and dose reductions or escalations of 5-azacytidine beyond those mentioned in table 5 or different to the doses specified should be discussed with the PI and documentation of the justification recorded in the chart.

5.2.1.3 The dose and /or schedule of administration is subject to modification pending information from ongoing clinical trials of lirilumab as a single agent and in combination with other drugs.

DLT is defined as clinically significant non-hematologic adverse event or abnormal laboratory value assessed as unrelated to disease progression, intercurrent illness, or concomitant medications and occurring during the first cycle on study that meets any of the following criteria:

- CTCAE Grade 3 AST (SGOT) or ALT (SGPT) for ≥ 7 days
- CTCAE Grade 4 AST (SGOT) or ALT (SGPT) of any duration
- All other clinically significant non-hematological adverse event that is Grade 3 or 4 according to the NCI common terminology criteria version 4.0 with the following exceptions:
 - Grade 3 or 4 nausea, vomiting and diarrhea will be considered DLT only if not controlled by optimal therapy.
 - Grade 3 biochemical abnormalities (e.g., lipase or bilirubin elevation) will only be considered DLT if accompanied by clinical consequences. Grade 3 or 4 electrolyte abnormalities will only be considered DLT if possibly related to study drug and not corrected by optimal replacement therapy.

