11.1 Sample Size

Part a. Lead-in phase

The primary objective of the lead-in phase is to determine the safety of lirilumab in combination with 5-azacytidine in patients with refractory/ relapsed AML. Up to 24 patients will be accrued into lead-in part of the study.

Part b. Phase II

Up to 40 patients (including 6 patients treated at the MTD from the lead-in part) will be recruited for the Phase II part.

The primary objective of the phase II is to determine the efficacy of lirilumab in combination with 5-azacytidine in patients with refractory, relapsed or untreated AML. The efficacy of the combination will be measured by the overall response rate (ORR), defined as CR (complete remission) + CRp (complete remission with incomplete platelet recovery) + CRi (complete remission with incomplete count recovery) + PR (partial response) + marrow clearance of blasts + HI (Hematological improvement) within 3 months of treatment initiation among adult patients with refractory/ relapsed AML. ORR and toxicity will be monitored simultaneously using the Bayesian approach of Thall, Simon, Estey (1995, 1996) and the extension by Thall and Sung (1998).

Once safety of the MTD has been established, any patients still on study at a dose lower than MTD can be dose escalated up to MTD. Patients treated in the lead-in phase at MTD will be included in the phase II portion of the study.

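### Section 5.3.7.4 lets the lirilumab dose rise in patients with cytopenias, against the phase II bar and the dose ceiling in section 5.3.6

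*Combined protocol and SAP*

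**What the plan says.** Four provisions of the combined protocol and SAP govern whether the lirilumab dose may change once phase II has begun.

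- **Section 5.2.1** (schedule): "There will be no dose reductions (only interruptions when indicated) allowed for lirilumab on this trial".
- **Section 5.2.1.2** (below Table 1): "For potential lirilumab related AEs in the phase II portion of the study only dose interruptions of lirilumab will be permitted". The same paragraph says that 5-azacytidine may still be reduced or escalated in phase II.
- **Section 5.3.6** (intra-patient re-escalation of 5-azacytidine): "Once the MTD has been established in the lead-in, the lirilumab dose will not be reduced or escalated during the phase II". It then lists conditions for raising 5-azacytidine again and ends with a ceiling: "No dose escalation beyond dose level 0 will be permitted".
- **Section 5.3.7.4** (other interruptions and modifications): one drug alone may be adjusted or delayed if the investigator attributes the toxicity to that drug. Two examples follow in parentheses. In autoimmune thyroiditis or hepatitis, attributed to lirilumab, the 5-azacytidine dose could go up. In cytopenias, "this would be likely secondary to 5-azacytidine and lirilumab dose could be escalated".

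**The concern.** A clinician following 5.3.7.4 could raise lirilumab in a phase II patient with cytopenias. A clinician following 5.3.6 could not. Both passages are operative dosing text for an investigational drug.

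Two things are at stake. The first is safety: read literally, a patient with current toxicity could be given more of the other drug, above the dose that the lead-in selected. The second is interpretation. Phase II is meant to describe the overall response rate and the drug-related grade 3/4 toxicity rate at the MTD, and section 11.2 monitors both. Lirilumab increases in some patients would mix doses within those counts.

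The trigger is not obviously rare. Section 5.6 expects myelosuppression in this population and says that most patients enter with neutropenia, thrombocytopenia or both.

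**Working it through.** No sample size, power or error rate is involved. The check sets the passages side by side and traces Table 1.

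**Step 1. Do the passages conflict?** Section 5.3.6 forbids lirilumab escalation in phase II and gives no exception. Section 5.3.7.4 allows it in cytopenia and is not confined to the lead-in. The same act is forbidden by one and permitted by the other. Section 5.3.1, which covers hematologic events directly, discusses interrupting or continuing lirilumab and rules out reducing it. It does not mention raising it.

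**Step 2. Could the increase merely restore a reduced dose?** No. Sections 5.2.1, 5.2.1.2, 5.3.1, 5.3.2 and 5.3.3 all exclude lirilumab reductions in phase II. A phase II patient is therefore at the MTD dose of lirilumab or has it interrupted, and any increase goes above the MTD dose.

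**Step 3. How large is the step?** Inputs are Table 1 (5-azacytidine in mg/m²/day, lirilumab in mg/kg) and the lead-in rule in 5.2.1.4: start at level -1, go to level 0 if 0 or 1 of 6 patients have a DLT, otherwise step down.

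| MTD | Dose at MTD (5-aza / lirilumab) | Next level up | Lirilumab ratio | Status of that level |
|---|---|---|---|---|
| 0 | 75 / 3.0 | none | n/a | barred by the level 0 ceiling |
| -1 | 75 / 1.0 | 75 / 3.0 | 3.0/1.0 = 3 | failed (at least 2 of 6 with DLT) |
| -2 | 75 / 0.3 | 75 / 1.0 | 1.0/0.3 = 3.3 | failed (at least 2 of 6 with DLT) |
| -3 | 50 / 0.3 | 75 / 0.3 | 0.3/0.3 = 1 | lirilumab unchanged |
| -4 | 25 / 0.3 | 50 / 0.3 | 0.3/0.3 = 1 | lirilumab unchanged |

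Level -1 can be the MTD only if level 0 was tried and failed, and level -2 only if level -1 failed. That is why the next level is a failed one in those two rows. For an MTD of -3 or -4, the adjacent level does not raise lirilumab, so raising it alone would give a pair of doses that Table 1 does not contain. The same holds in any row if 5-azacytidine has been reduced at the same time.

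**Step 4. The 5-azacytidine example.** Here there is no flat bar, because 5.2.1.2 keeps escalation open. But 5.3.6 makes re-escalation conditional on, among other things, a completed cycle at the current dose and no grade 3 or higher non-hematologic drug-related toxicity. Section 5.3.7.3 asks for at least a month free of toxicity requiring adjustment. Table 2 holds both drugs for grade 3 or 4 events. The example in 5.3.7.4 refers to none of these.

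**The case against.** **It is only an example, and the investigator is overseen.** The operative sentence of 5.3.7.4 allows adjustment or delay of one agent, and the escalation wording sits in a parenthesis. The preceding sentence requires discussion with the PI and a documented rationale. The word may well be a drafting slip. All of this is fair and bears on how often the example would be acted on. It does not remove the conflict: the bar in 5.3.6 has no PI exception, and the sentence that carries the examples rests on the investigator's attribution.

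**Section 5.3.7.4 covers only modifications not mentioned earlier.** Lirilumab escalation in phase II was mentioned earlier, and prohibited.

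**The level 0 ceiling limits the harm.** It does if 5.3.6 is followed. But when the MTD is level 0, that ceiling is a second provision that 5.3.7.4 contradicts. When the MTD is lower, the ceiling does not stop a step above the MTD.

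**A stronger reading that a reader might infer** is that section 11.1 also contradicts 5.3.6, since it says that "any patients still on study at a dose lower than MTD can be dose escalated up to MTD". By the path in 5.2.1.4, the only assigned lead-in cohort that can lie below the MTD is level -1 when the MTD is level 0. Those levels differ only in lirilumab (1.0 against 3.0 mg/kg), so for that cohort 11.1 does mean more lirilumab. But the bar in 5.3.6 is worded for phase II, and the next sentence of 11.1 brings into phase II only lead-in patients treated at the MTD. Patients below it can be read as outside phase II, so both rules can stand. Moving those patients to the MTD also cannot take them above it. What is missing is at most a cross-reference.

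**A reader might also infer** that such patients could slip into the phase II count. The documents already fix it: 6 lead-in patients at the MTD plus the 34 added under 5.2.1.4 make the 40 of section 11.1.

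**Conclusion.** The point holds for lirilumab in phase II. Section 5.3.7.4 permits what 5.3.6 forbids and goes against the interruption-only rule in 5.2.1.2. Any increase made under it would exceed the MTD: by a factor of 3 to 3.3, to a level that failed the DLT rule, if the MTD is level -1 or -2; and beyond the study ceiling if the MTD is level 0. These figures take Table 1 as the dose ladder and assume that the increase follows its next step with 5-azacytidine at that level's dose. Section 5.3.7.4 itself names no step.

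The 5-azacytidine example is a lesser matter: it needs aligning with existing conditions and does not breach a flat prohibition.

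The number of patients affected cannot be derived. The sample size of 40 and Tables 4 to 6 are unchanged. The matter should be corrected because it concerns patient safety and which dose the phase II results describe.

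**What to change.** Reconcile 5.3.7.4 with 5.2.1.2, 5.3.6 and 5.3.7.3 in a single statement of whether, when and for whom the dose of either drug may rise, and make the two examples in 5.3.7.4 agree with it. Which clinical rule applies is for the sponsor to decide. A cross-reference between 11.1 and 5.3.6 would make clear that the two address different patients. The cost is amendment wording, with no change to sample size, stopping boundaries or analysis.
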